1.2 Study Design

Study AMAX is a long-term study of participants completing Studies I6T-MC-AMAM (Study AMAM) and I6T-MC-AMAG (Study AMAG) (see schema below).

Two intervention groups will be studied in participants with moderate-to-severe CD:

Mirikizumab CCI

Mirikizumab CCI

Q4W; CCI

Q4W; CCI

Q4W; 900 mg is the induction dose being studied in Study AMAM.

Study participants will receive mirikizumab for an extended period of time (approximately 3 years or until commercial availability of mirikizumab, whichever comes first) and then enter a 12- to 16-week posttreatment follow-up period. After completion of the long-term extension period, if mirikizumab is not yet locally commercially available and reimbursable, eligible participants will be provided with an option of continued access to open-label mirikizumab, and then enter CCI follow-up period

Study AMAM participants will require an endoscopy to be performed at Week 52, CCI

Study AMAM participants will require an endoscopy to be performed at Week 52, CCl visit occurs more than 16 weeks after the last endoscopy in Study AMAX.

Study AMAG participants who are entering Study AMAX after completing CCI into Study AMAX.

Participants who have not yet completed CCI

Study intervention may be permanently discontinued or temporarily withheld during the study (see Sections 7.1.1 and 7.1.2 of the AMAX Protocol). Participants who permanently discontinue study drug early will undergo early termination procedures, which include an early termination visit (ETV) and post-treatment follow-up visits (V801 and V802).

No rescue medication is allowed during the study. Participants who enter Study AMAX on corticosteroids should initiate corticosteroid tapering as described in the protocol (see Section 6.5.3 of the AMAX Protocol).

An interim analysis of the co-primary endpoints may be conducted when all Study AMAM participants complete Week 52 of Study AMAX. Additional ad-hoc interim analyses may be performed as deemed appropriate or to fulfill the need of regulatory interactions or publication purposes.

A Data Monitoring Committee (DMC) consisting of members external to Lilly will be established for interim safety monitoring across all the sponsor's adult Phase 3 studies in participants with CD. Additional details can be found in the AMAX protocol (see Section 10.1.5) and in the DMC Charter.

The final database lock will occur after the last participant has completed Study AMAX.

2 Statistical Hypotheses

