5.1.1 Analysis Methods

Unless otherwise specified, efficacy analyses will be conducted on PAS population, and safety analyses will be conducted on the safety populations as described in Section 4. Summaries will be presented by intervention group in Study AMAX and by the intervention received in the originating study.

Descriptive statistics will include the number of participants; mean, standard deviation, median, minimum, and maximum for continuous measures; and frequency counts and percentages for categorical measures.

For assessments of the co-primary endpoints and other binary efficacy and health outcomes endpoints, the following will be provided unless otherwise specified:

• unadjusted proportions along with the 2-sided 95% confidence intervals using the Wilson Score method (Wilson 1927; Newcombe 1998).

The primary method for binary endpoints will utilize the Wilson Score method. Additional missing data imputation methods for binary endpoints are specified in Section 5.1.5.

For continuous endpoints with more than one post baseline timepoint, the least squares mean from a restricted maximum likelihood based mixed effects model of repeated measures (MMRM) with the corresponding 95% confidence interval may be summarized. The MMRM model will include baseline value, intervention group (Section 5.1.4), visit, and visit by intervention group interaction. Alternative versions of MMRM may be implemented as deemed appropriate. The covariance structure to model the within-participant errors will be unstructured. If the unstructured covariance matrix results in a lack of convergence, the heterogeneous

Toeplitz covariance structure followed by the heterogeneous autoregressive covariance structure will be used. The Newton-Raphson with ridging optimization technique will be used to aid with convergence. The Kenward-Roger method will be used to estimate the denominator degrees of freedom. If the listed methods result in a lack of convergence, analysis may be limited to data through Week 52 of Study AMAX. Following, the model may be updated to remove the visit by intervention received in Study AMAM interaction. If the model fails to converge after the interaction term has been removed, MMRM may not be used for analysis. Unless otherwise specified the MMRM analysis will be performed only for patients originating from AMAM.

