For variables that are not collected at each postbaseline visit, data may exist at visits where the variable was not scheduled to be collected. In these situations, data from the early discontinuation visit that do not correspond to the planned collection schedule will be excluded from the MMRM analysis (Andersen and Millen 2013). As the MMRM method accounts for missing data under the missing at random assumption, no other missing data techniques will be used with the MMRM model.

For all change from baseline measures of continuous efficacy, health outcomes, and quality of life endpoints, the least squares mean and the corresponding 95% confidence interval from analysis of covariance (ANCOVA) will be summarized. The ANCOVA model will include baseline value, and intervention group (see Section 5.1.4) in the model. Additional continuous endpoints that are not change from baseline will be presented as summaries. Unless otherwise specified the ANCOVA analysis will be performed only for patients originating from CCI.

Missing data imputation method for the ANCOVA model and summaries are specified in Section 5.1.5.

All analyses of safety data will be presented as summaries.

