5.6 Safety Analyses

In general, safety evaluations will be based on the Safety Population for the Induction Period and Complete Study Period. Select safety analysis will also be performed for the continued access period as needed.

For the purpose of Study AMAX alone, the following are planned:

- Listing of Serious Adverse Events (SAEs)
- Listing of adverse events leading to permanent discontinuation of study drug
- Summary of SAEs (with different columns for the intervention groups specified in Section 5.1.4)
- Summary of AEs leading to permanent discontinuation of study drug (with different columns for the intervention groups specified in Section 4)

The safety data from this study will also be used as part of ongoing safety reviews. The safety data from this study will also be used as part of integrated summaries in submissions/disclosures and ongoing safety review through study end.

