5.6.1 Extent of Exposure

Duration of exposure to study intervention will be summarized by study intervention group for the Safety Population. For the Complete Study Period, exposure will be calculated as (Date of end date of Complete Study Period – Date of start date of the Complete Study Period + 1 day) described in Section 5.1.3. Calculations will use the Safety Population in the Complete Study Period.

Total participant-years (PY) of exposure will be reported for the Safety Population by study intervention group in Section 4. Descriptive statistics will be provided for participants-weeks of exposure and the frequency of participants falling into different exposure ranges will be summarized.

- >0; ≥12 weeks; ≥36 weeks; ≥52 weeks; ≥68 weeks; ≥84 weeks; ≥100 weeks; ≥116 weeks; ≥140 weeks;
- >0 to <12 weeks; \geq 12 weeks to <36 weeks; \geq 36 weeks to <52 weeks; \geq 52 weeks to <68 weeks; \geq 68 weeks to <84 weeks; \geq 84 weeks to <100 weeks; \geq 100 weeks to <116 weeks; \geq 116 weeks to <140 weeks; \geq 140 weeks

Additional exposure ranges may be considered, if necessary. No p-values will be reported in these tables as they are intended to describe the study populations, rather than test hypotheses about them.

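### Over the Complete Study Period, SAEs and AE discontinuations are summarised by group with no exposure-adjusted statistic, so crude percentages can mislead if follow-up differs

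*SAP*

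**What the plan says.** SAP 5.6 lists four outputs for AMAX alone: two listings, a "Summary of SAEs (with different columns for the intervention groups specified in Section 5.1.4" and a "Summary of AEs leading to permanent discontinuation of study drug (with different columns for the intervention groups specified in Section 4". No rate, person-time or time-to-event statistic is named for either summary. SAP 5.1.1 sets the default for such data as "frequency counts and percentages for categorical measures" and adds that "All analyses of safety data will be presented as summaries".

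Exposure is handled separately, in SAP 5.6.1: "Total participant-years (PY) of exposure will be reported for the Safety Population by study intervention group in Section 4". The same section says that "the frequency of participants falling into different exposure ranges will be summarized", with bands from under 12 weeks to 140 weeks or more. Nothing links these quantities to the event summaries. The registry output in SAP Appendix 6 gives participants at risk, participants with the event and event counts, again without person-time.

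Treatment lasts "approximately 3 years or until commercial availability of mirikizumab, whichever comes first" (SAP 1.2). The Complete Study Period in SAP 5.1.3 runs from first dose to the last planned treatment visit or to discontinuation.

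**The concern.** The share of people with at least one event rises with time observed. If two columns have different follow-up, their percentages differ even when the underlying risk is the same, and a real difference can be hidden or reversed.

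The design gives reasons to expect unequal follow-up:
- SAP Section 2 assigns AMAM participants to SC, or to IV then SC, by endoscopic response at AMAM Week 52. The columns in SAP 5.1.4 therefore separate prior responders from non-responders.
- Protocol 7.1.2 lets participants and physicians stop if they see no benefit, which could be commoner in some columns than in others.
- Protocol 10.15.4 withdraws Hungarian participants who were on placebo and considered responders at AMAM Week 52. That shortens follow-up in one kind of column, and it is a responder column.

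At stake is how the SAE and AE-discontinuation tables in the AMAX report will be read. Protocol 9.4.4 commits to these tables for that report.

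**Working it through.** The plan states no SAE rate, AE-discontinuation rate or participant-year total, so there is no figure to reproduce. Event rates and follow-up patterns below are assumptions. The 52- and 156-week points are the Week 52 and Week 156 visits in SAP Appendix 9; days convert to years at 365.25, as in SAP 5.1.3.

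**Formulas.** T = weeks × 7 / 365.25, so 52 weeks = 0.997 years and 156 weeks = 2.990 years. With constant rate λ and everyone followed for T, crude proportion = 1 − exp(−λT). Exposure-adjusted rate = participants with a first event ÷ participant-years up to first event or end of period.

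**Same true rate, different follow-up**

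| Assumed rate per 100 PY | All followed 52 weeks | All followed 156 weeks | Adjusted rate, both |
|---|---|---|---|
| 5 | 4.9% | 13.9% | 5.0 |
| 10 | 9.5% | 25.8% | 10.0 |
| 15 | 13.9% | 36.1% | 15.0 |

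**Milder case.** At 10 per 100 PY with 40% stopping at 52 weeks: 0.6 × 25.8 + 0.4 × 9.5 = 19.3%, against 25.8% with full follow-up. The ratio is 1.3, compared with 13.9 / 4.9 = 2.8 in the extreme case at 5 per 100 PY.

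**A real difference reversed.** A group with 10 per 100 PY followed 52 weeks shows 9.5%. A group with half that rate followed 156 weeks shows 13.9%.

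**When AEs cause the stopping.** Take AE-discontinuation rates of 10 and 3 per 100 PY over a planned 156 weeks. The crude percentages are 25.8% and 8.6%. The group that stops earlier has the higher percentage, and its risk is in fact higher.

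**Front-loaded risk.** Give both groups 40 per 100 PY to Week 12 and 5 afterwards. The crude percentage is 20.5% at 156 weeks and 12.2% at 52 weeks. A single adjusted rate is 8.0 and 13.5 per 100 PY, so it reverses the apparent order although the hazards are identical. Rates split at Week 12 would be 40 and 5 in both groups.

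**Why total participant-years is the wrong denominator for first events.** At 10 per 100 PY, 100 people followed 156 weeks give 299.0 total PY but only 25.84 / 0.10 = 258.4 PY at risk. Dividing by total PY gives 25.84 / 2.990 = 8.6 per 100 PY. The 52-week group gives 9.485 / 0.997 = 9.5. Both should be 10.0.

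**Short windows.** If everyone completes 12 weeks, the crude percentage is 1.1% to 3.4% at 5 to 15 per 100 PY, so follow-up differences matter little there.

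**The case against.** The strongest reply is that these are minimal descriptive tables. Protocol 9.4.4 says safety is better judged by combining AMAX with the originating studies, and SAP Section 2 rules out intervention comparisons. Participant-years and exposure bands appear by group, so any imbalance is visible, and SAEs are listed individually. Safety is also evaluated over the Induction Period, and SAP 5.8.3 uses a 1-year safety period for the September 2024 interim; both limit differences in follow-up. The table specifications sit in a separate document (SAP Section 1) and may already contain rates.

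Much of this stands. It confines the point to the Complete Study Period and lowers its weight. It does not remove it: the tables are committed for the AMAX report, adjacent columns invite comparison, and a first-event rate cannot be recovered from total participant-years. The SAP, rather than the shells alone, should name the statistic.

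A reader might also infer that groups with early stopping will look safer. The documents do not support that. It requires stopping unrelated to the events and a roughly constant hazard, and for AE discontinuation the event is itself the stopping. Nor do they show that the IV columns have poorer retention. The assignment rule is stated but no retention figures are, commercial availability acts by country, and the one clearly legible group-specific withdrawal rule concerns placebo responders.

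**Conclusion.** The point holds in a limited form. For the Complete Study Period the SAP specifies no exposure-adjusted summary of SAEs or of AEs leading to discontinuation, and its default statistic mixes risk with length of follow-up. The distortion can favour either column, depending on which has the shorter follow-up and why people stop.

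Its size cannot be stated from the documents. The near three-fold contrast needs everyone in one group to stop at 1 year and everyone in the other to reach 3 years. The 1.3-fold case, with 40% stopping at 52 weeks, shows how far the figure depends on the assumed pattern. All figures rest on assumed rates.

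It would be too strong to say that the tables mislead on the study's main safety purpose, because the protocol places that purpose in integrated assessments. This is a minor point and a cheap improvement.

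**What to change.** In SAP 5.6, for the Complete Study Period and by the SAP 5.1.4 groups, add to both summaries, beside the counts:
- participants with a first event per 100 participant-years at risk, with 95% CIs, time censored at first event, and the event window matched to the exposure window (state whether events in the separate Follow-up Period count);
- rates by time window, for example to Week 12, Week 12 to 52 and after Week 52, or a cumulative incidence estimate, in case risk is front-loaded.

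Total participant-years from SAP 5.6.1 should be used only for rates based on event counts.

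Also change the group references to Section 4 in SAP 5.6 and 5.6.1 to Section 5.1.4. Section 4 defines analysis sets and itself points to 5.1.4 for the treatment arms.

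The cost is one extra derivation, time to first event, and a few table columns. No new data are needed.

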5.6.1 Extent of Exposure

Duration of exposure to study intervention will be summarized by study intervention group for the Safety Population. For the Complete Study Period, exposure will be calculated as (Date of end date of Complete Study Period – Date of start date of the Complete Study Period + 1 day) described in Section 5.1.3. Calculations will use the Safety Population in the Complete Study Period.

Total participant-years (PY) of exposure will be reported for the Safety Population by study intervention group in Section 4. Descriptive statistics will be provided for participants-weeks of exposure and the frequency of participants falling into different exposure ranges will be summarized.

- >0; ≥12 weeks; ≥36 weeks; ≥52 weeks; ≥68 weeks; ≥84 weeks; ≥100 weeks; ≥116 weeks; ≥140 weeks;
- >0 to <12 weeks; \geq 12 weeks to <36 weeks; \geq 36 weeks to <52 weeks; \geq 52 weeks to <68 weeks; \geq 68 weeks to <84 weeks; \geq 84 weeks to <100 weeks; \geq 100 weeks to <116 weeks; \geq 116 weeks to <140 weeks; \geq 140 weeks

Additional exposure ranges may be considered, if necessary. No p-values will be reported in these tables as they are intended to describe the study populations, rather than test hypotheses about them.

5.6.2 Immunogenicity

Immunogenicity will be evaluated cumulatively, using data both from the participant's originating study and from the present study. Baseline for ADA assessment will be the baseline ADA assessment from the originating study, and postbaseline will be time after initiation of mirikizumab.

An individual sample is potentially examined multiple times in a hierarchical procedure to produce a sample anti-drug antibodies (ADA) assay result and potentially a sample neutralizing anti-drug antibodies (NAb) assay result. A participant has treatment-emergent anti-drug antibodies (TE-ADA) when ADA are induced or boosted by exposure to study drug; i.e., when at least one postbaseline ADA sample has a 4-fold increase in titer, compared to baseline (if ADA were present at baseline) or has a titer 2-fold greater than the minimum required dilution of 1:10 (if no ADA were present at baseline).

Compound level safety standards will be followed in the analyses of immunogenicity. The summary of TE ADA positive (TE ADA+), TE ADA+ by titers and TE ADA+ with neutralizing antibody (NAb) status to mirikizumab will be produced for the mITT population (including originating studies and Study AMAX).

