Participants who are CCI [REDACTED]

[REDACTED] will receive open-label mirikizumab subcutaneously (SC) for an extended period of time (up to 3 years) and then enter a 12- to 16-week posttreatment follow-up period. Participants who are CCI [REDACTED]

will receive CCI [REDACTED] of mirikizumab CCI [REDACTED]

[REDACTED] After completion of the long-term extension period, if mirikizumab is not yet locally commercially available and reimbursable, eligible participants will be provided with an option of continued access to open-label mirikizumab, followed by a CCI [REDACTED] follow-up period. The duration of the continued access will differ by participant and country.

Participants who meet all of the inclusion criteria and none of the exclusion criteria of AMAX, and who, in the opinion of the investigator, would receive benefit from open-label treatment with mirikizumab are eligible for enrollment into Study AMAX. It is possible that some participants enrolling from Study AMAM may have received placebo only in the originating study. These participants will receive mirikizumab for the first time in Study AMAX.

Brief Summary:

This is a long-term extension treatment study with participants who have been previously or are currently diagnosed with moderately-to-severely active CD.

Participants from Study AMAM: All incoming participants irrespective of AMAM treatment assignment (mirikizumab, ustekinumab, or placebo) are CCI [REDACTED]

- CCI [REDACTED]
- CCI [REDACTED]

CCI [REDACTED]

Study Population:

In general, an individual may take part in Study AMAX if the individual

- has completed the last visit of participation in Study AMAG, remained on mirikizumab treatment in either the maintenance dosing period or in Study AMAG extension period, and in the opinion of the investigator, would derive clinical benefit from continued treatment with mirikizumab, OR
- has completed Week 52 of Study AMAM, including the Week 52 endoscopy CCI [REDACTED], and in the opinion of the investigator, would derive clinical benefit from treatment with mirikizumab.

Number of Participants:

The final sample size of Study AMAX will be determined by the number of participants who enroll in Study AMAX from the preceding studies (AMAM and AMAG). It is anticipated that approximately 50% to 70% of the participants from Studies AMAM and AMAG will enroll, leading to approximately 640 to 900 participants in Study AMAX.

Intervention Groups and Duration:

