1.3. Schedule of Activities (SoA)

1.3.1. Visit 1 through Visit 9 CCI

Table AMAX.1-1. Schedule of Activities - Visit 1 through Visit 9 CCI

Procedures	Schedule of Activities ^a										
Visit Number	V1 ^b		V2	V3	V4		V5	V6	V7	V8	V9
Visit Type	Office – Screening/ V1 ^a	Office - Dosing/V1 ^b	Office	Office	Phone	Office	Office	Office	Office	Office	Office
Week Relative to Study Drug Start ^c	CCI										
Day with Visit Tolerance Interval (VTI)											
All Participants (X); AMAM Rollover Participants Only (M); AMAG Rollover Participants Only (G); Optional (Opt) (See footnotes for additional key details)											
Informed consent	X										
Preexisting conditions	X	X									
Inclusion/Exclusion Criteria	X										
Concomitant medications	X ^{ae}	X	X	X		X	X	X	X	X	
Tobacco/Nicotine use	X ^f					X				X	
Demographics	X ^f										
AEs ^g (See Section 8.3)	X ^{ae}	X	X	X		X	X	X	X	X	
Phone Reminder ^e					X					X	
Physical Evaluation											
Vital signs (T, PR, BP) (See Section 8.2.1.)	X ^{ac, ag}	X ^{ag}	X	X		X	X	X	X	X	
Weight	X ^{af}					X				X	
Physical examination ^h (See Section 8.2.2.)	X ^{ae}	X	X	X		X	X	X	X	X	
CCI [REDACTED]	X ^f	X ^{ah}	X	X		X	X	X	X	X	
CCI [REDACTED]	X ^f	X ^{ah}	X	X		X	X	X	X	X	
Clinician CDAI (See Section 8.1.2.1.)	X ^{af}	X ^{ah}				X				X	
TB Risk Assessment Monitoring ⁱ	X ^{af}	X ^{ah}	X			X	X	X	X	X	

Procedures		Schedule of Activities ^a											
Visit Number	V1 ^b	V2		V3	V4		V5	V6		V7	V8	V9	
Visit Type	Office – Screening/ V1 ^a	Office - Dosing/V1 ^b	Office	Office	Phone	Office	Office	Office	Office	Office	Office	Phone	Office
Week Relative to Study Drug Start ^c	CCI												
Day with Visit Tolerance Interval (VTI)													
Laboratory Tests													
Chemistry	X ^{af}	X ^{ah}	X	X		X	X	X	X	X	X		X
Hematology	X ^{af}	X ^{ah}	X	X		X	X	X	X	X	X		X
Urine Pregnancy (local) ^j (See Section 8.2.7.1.)	X	X	X	X		X	X	X	X	X	X		X
Urinalysis	X ^k												
HIV testing	X												
HBV screening ^l (Section 8.2.8.)	X												
HBV DNA monitoring ^m	X ^{af}	X ^{ah}	X			X	X	X	X	X			X
HCV testing (See Section 8.2.9.)	X												
PK sample ⁿ	X ^{af}	X ^{ah}				X				X			X
Immunogenicity (ADA) samples ⁿ	X ^{af}	X ^{ah}				X			X				X
CCI	X ^f	X ^{ah}				X			X				X
Stool Samples (Note: Additional local stool testing [for example, ova and parasites] is allowed at the investigator's discretion.)													
Fecal calprotectin ^o	X ^f	X ^{ah}				X			X				X
Dispense stool collection kit ^o										M			

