5.1. Inclusion Criteria

Participants are eligible to be included in the study only if all of the following criteria apply. Criteria below apply to all AMAX participants, regardless of their originating study, unless a specific originator study (AMAM or AMAG) is specified:

Informed Consent

[1] Have given written informed consent approved by the ethical review board (ERB) governing the site.

Type of Participant and Disease Characteristics

[2] Participants from the Phase 2 Study AMAG who:

- completed the last visit of participation in the AMAG study and remained on mirikizumab treatment in either the maintenance dosing period 3 or in the AMAG extension period, and
- in the opinion of the investigator, would derive clinical benefit from continued treatment with mirikizumab.

It is recommended that participants receive the first dose of AMAX study drug within approximately CCI [REDACTED] of the last dosing visit in AMAG. A maximum of CCI [REDACTED] will be allowed between the last dose in AMAG and the first dose in AMAX to accommodate situations where due to circumstances outside the patient's control, a patient may not be able to complete all required assessments within the recommended shorter window.

OR

[3] Participants from the Phase 3 Study **AMAM** who:

- completed Week 52 of the AMAM study, including the Week 52 endoscopy [REDACTED], and in the opinion of the investigator would derive clinical benefit from treatment with mirikizumab.

It is recommended that participants receive the first dose of AMAX study drug within approximately [REDACTED] CCI [REDACTED] after the last dosing visit in AMAM. A maximum of [REDACTED] CCI [REDACTED] will be allowed between the last dose in AMAM and the first dose in AMAX to accommodate situations where due to circumstances outside the patient's control, a patient may not be able to complete all required assessments within the recommended shorter window.

Note: Participants who have completed the AMAM adolescent addendum are not eligible for the AMAX trial, but may be eligible for the pediatric IBD long-term extension trial.

Participant Characteristics

[4] Are willing and able to complete the scheduled study assessments, including endoscopy, self-administer investigational product (or have caregiver administer investigational product), and complete patient electronic and paper diary (See Section 8.1.2.2).

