9.4.6. Evaluation of Immunogenicity

Immunogenicity will be evaluated cumulatively, using data both from the participant's originating study and from the present study. Baseline for ADA assessment will be the baseline ADA assessment from the originating study, and postbaseline will be time after initiation of mirikizumab.

The frequency and percentage of participants with pre-existing (baseline) ADA, ADA postbaseline, and with TE ADA to mirikizumab will be tabulated. If no ADAs are detected at baseline, TE ADAs are defined as those with a titer 2-fold (1 dilution) greater than the minimum required dilution of the assay. For samples with ADAs detected at baseline, TE ADAs are defined as those with a 4-fold (2 dilutions) increase in titer compared to baseline. For participants who have TE ADAs, the distribution of maximum titers will be described.

The frequency of neutralizing antibodies will also be tabulated. The relationship between the presence of antibodies and the PK parameters and pharmacodynamic response, including safety and efficacy to mirikizumab, will be assessed as deemed appropriate.

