5.1.4 Definition of Study Intervention by Study Period

The table below provides the study intervention groups to be displayed for each analysis population and analysis period.

Analysis	Analysis Period	Study Intervention Groups:
Population		
PAS/mITT/Safety population	Induction Period/Complete Study Period/ Continued Access Period	 AMAM miri/miri/ SC AMAM pBO/miri/ SC AMAM PBO/miri/ IV AMAM PBO/miri/ IV AMAM uste/uste/ SC AMAM uste/uste/ IV AMAM PBO/PBO/ SC AMAM PBO/PBO/ IV AII AMAM/ SC a All AMAM/ IV a All AMAM a All AMAM/ SC a Total a
PAS/mITT subset populations	Complete Study Period	PAS/mITT sub-population – Endoscopic Responder in the originating study: • AMAM miri/miri/ SC (co-primary analysis) • AMAM PBO/miri/ SC • AMAM uste/uste / SC • AMAM PBO/PBO/ SC • All AMAM SC a • Total a PAS/mITT sub-population – Endoscopic Nonresponder in the originating study: • AMAM miri/miri / IV • AMAM PBO/miri/ IV • AMAM uste/uste / IV • AMAM PBO/PBO/ IV • AMAM PBO/PBO/ IV • All AMAM IV a • Total a

Analysis Population	Analysis Period	Study Intervention Groups:		
		Other sub-population analysis:		
		 AMAM miri/miri/ SC AMAM miri/miri/ IV AMAM PBO/miri/ SC AMAM PBO/miri/ IV AMAM uste/uste/ SC AMAM uste/uste/ IV AMAM PBO/PBO/ SC AMAM PBO/PBO/ IV AII AMAM/ SC a All AMAM/ IV a All AMAM a All AMAM a Total a 		

Abbreviations: AMAG = Study I6T-MC-AMAG; AMAM = Study I6T-MC-AMAM; IV = intravenous; miri = mirikizumab; PBO = placebo; SC = subcutaneous; uste = ustekinumab; Q4W = every 4 weeks.

For endpoints utilizing the PAS/mITT subset populations, not all intervention groupings listed above may be shown.

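### For participants first given mirikizumab in AMAX, treatment-emergent ADA is judged against a sample at least about 52 weeks old, although a pre-dose sample near first exposure is already scheduled

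*SAP*

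**What the plan says.** SAP 5.6.2 sets the rule: "Baseline for ADA assessment will be the baseline ADA assessment from the originating study, and postbaseline will be time after initiation of mirikizumab". Protocol 9.4.6 has the same rule ("Baseline for ADA assessment will be the baseline ADA assessment from the originating study"). Neither makes an exception for participants who start mirikizumab in AMAX.

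SAP 5.6.2 describes treatment-emergent ADA (TE-ADA) as ADA caused or raised by study drug, and makes this operational in two branches. One applies "when at least one postbaseline ADA sample has a 4-fold increase in titer, compared to baseline (if ADA were present at baseline"). The other applies when a postbaseline sample "has a titer 2-fold greater than the minimum required dilution of 1:10 (if no ADA were present at baseline").

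Participants new to mirikizumab do enter AMAX. Protocol 1.1 says of AMAM participants who had placebo only: "These participants will receive mirikizumab for the first time in Study AMAX". The intervention groups in SAP 5.1.4 include PBO/PBO and uste/uste, each with SC and IV rows, for example "AMAM uste/uste/ SC". AMAM entrants must have "completed Week 52 of the AMAM study, including the Week 52 endoscopy" (Protocol 5.1).

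The Year 1 schedule (Protocol 1.3.1) has a row for "Immunogenicity (ADA) samples" marked at both V1a and V1b. By its footnotes, the sample is drawn before dosing. It is taken at V1a unless the last originator visit already supplied it, and it is repeated before V1b dosing if the last one is too old. That interval is redacted in the main schedule; the Czech version of the same footnote (Protocol 10.15.3) gives 14 weeks.

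**The concern.** A TE-ADA call should compare titres just before and after the drug starts. For PBO/PBO and uste/uste participants the plan leaves about a year on placebo or ustekinumab between the baseline sample and the start of the postbaseline period. Samples from that year count as neither baseline nor postbaseline, yet a change that occurred then still enters the comparison if it lasts. The rule can therefore depart from the SAP's own description of TE-ADA, in either direction.

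At stake is the TE-ADA classification of participants whose first mirikizumab exposure is in AMAX, in any display by the treatment sequences of SAP 5.1.4. The efficacy analyses are not touched.

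**Working it through.** The documents give no TE-ADA figure to reproduce, so the check applies the SAP's rule with each candidate baseline.

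**Age of the baseline.** The AMAM baseline sample is at AMAM Week 0, and entry to AMAX requires completion of AMAM Week 52. The gap is therefore at least about 52 weeks, plus an inter-study interval whose maximum is redacted.

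**Rule.** Let b be the originating-study titre, v the last titre before the first mirikizumab dose, and p the highest titre after mirikizumab starts, all as reciprocals. The threshold for a baseline x is:

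- T(x) = 2 × 10 = 20 if x is negative (minimum required dilution 1:10)
- T(x) = 4x if ADA are present

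The plan calls TE-ADA positive if p ≥ T(b). A pre-dose baseline calls it positive if p ≥ T(v). The two disagree only when p lies between the thresholds:

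- T(b) ≤ p < T(v): positive under the plan, negative against the pre-dose sample
- T(v) ≤ p < T(b): negative under the plan, positive against the pre-dose sample

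**Illustrative titres (assumed, not from the documents).**

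| b | v | p | T(b) | T(v) | Plan's baseline | Pre-dose baseline |
|---|---|---|---|---|---|---|
| negative | negative | 1:20 | 20 | 20 | TE+ | TE+ |
| 1:20 | 1:20 | 1:80 | 80 | 80 | TE+ | TE+ |
| negative | 1:20 | 1:20 | 20 | 80 | TE+ | TE− |
| negative | 1:20 | 1:40 | 20 | 80 | TE+ | TE− |
| negative | 1:20 | 1:80 | 20 | 80 | TE+ | TE+ |
| 1:40 | negative | 1:20 | 160 | 20 | TE− | TE+ |
| 1:40 | negative | 1:80 | 160 | 20 | TE− | TE+ |
| 1:40 | 1:20 | 1:80 | 160 | 80 | TE− | TE+ |

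In row 3 nothing changes after mirikizumab, yet the plan reports TE-ADA. In the last row the titre rises 4-fold on mirikizumab, yet the plan does not. Where the two pre-mirikizumab samples agree (rows 1 and 2), the choice of baseline is immaterial.

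**Size.** In a group of N participants, the net error in the TE-ADA rate is (number falsely positive − number falsely negative) / N. The documents supply none of these three quantities for PBO/PBO or uste/uste, so no value can be computed.

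**The case against.** The rule is deliberate and consistent. SAP and protocol agree, it is an explicit exception to the AMAX baseline that SAP 5.1.2 sets for safety analyses, and a common baseline suits an evaluation that pools the originating study with AMAX. For PBO/PBO and uste/uste the AMAM baseline also precedes any mirikizumab. All of this stands: it is an analysis choice, not a conflict between documents, and the sample is a valid pre-exposure one. Its weakness is its age.

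A reader might infer that every change in reactivity during the AMAM year is counted as caused by mirikizumab. The documents do not support that. Postbaseline begins only when mirikizumab starts, so titres measured on placebo or ustekinumab cannot themselves be TE-ADA. A false positive needs a shift that persists into the mirikizumab period and a postbaseline titre between the two thresholds. A false negative needs ADA at AMAM baseline, then waning, then a rise that stays below 4-fold of the old titre.

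A pre-dose baseline could also be called a trade-off: with titres negative, 1:20 and 1:40, a doubling after mirikizumab becomes TE-negative. That is only the SAP's own 4-fold threshold for pre-existing ADA, applied to the sample nearest first exposure.

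Finally, SAP 5.6.2 defers to compound-level safety standards, which might handle this case. They are not in the documents, and the explicit sentence in the SAP makes no exception.

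**Conclusion.** The concern holds for PBO/PBO and uste/uste participants. Their TE-ADA status is judged against a sample at least about 52 weeks older than first mirikizumab exposure, and the rule can misclassify in both directions when the titre moved before that exposure.

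The magnitude is unknown. It would be tempting to take a plausible share of participants changing ADA status and report that share as the error in the rate. The documents give no basis for one: ADA rates and the number of mirikizumab-naive entrants are both absent, many titre changes leave the call unchanged, and opposite errors partly cancel in a group rate.

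Participants on mirikizumab from AMAM Week 0 are unaffected. For PBO/miri the gap is shorter (Protocol 2.2.5 describes a switch at AMAM Week 12), and the documents do not show whether AMAM took an ADA sample before that switch, so no conclusion is drawn there.

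The analyses are descriptive, and no primary or secondary efficacy endpoint depends on this. The case for change is that the better sample is already scheduled. The verdict assumes that the pre-dose samples were collected as scheduled and that a titre 2-fold above the minimum dilution means 1:20 or higher.

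**What to change.** In SAP 5.6.2, define the ADA baseline for PBO/PBO and uste/uste participants as the last ADA sample before the first mirikizumab dose. That is the AMAX V1a or V1b pre-dose sample, or the last AMAM visit's sample where that one was used. Keep the originating-study baseline version as a sensitivity tabulation for these groups.

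For PBO/miri, apply the same rule only if AMAM collected an ADA sample before the switch; otherwise leave the baseline as it is.

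Record the change in SAP Appendix 3, which now states that there are no changes to protocol-planned analyses, and align Protocol 9.4.6 at the next amendment.

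Cost: one extra tabulation, and a documented departure from Protocol 9.4.6 until it is amended. PBO/PBO and uste/uste need no new samples.
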